15.3 Secondary Efficacy Measures

- Overall Survival Time (OS):
 - OS time will be measured from date of study entry to date of death from any cause. For those who are alive, we censor them at the time of loss to follow-up (very few) or at 30 months from the date of treatment discontinuation, which come first.
- Time to Progressive Disease (TTP):
 - TTP is defined as the time from study entry until date of radiographic PD using RECIST v1.1 criteria. For those who are alive and do not experience progression, we censor them at the time of loss to follow-up (very few) or at 12 months from the study entry, which come first. For those who are dead before progression, we will consider death as the competing risk. If the number of death are very small, we will censor them at time of death.
- Best Overall Response (BOR) of Complete Response (CR), Partial Response (PR), Stable Disease (SD) or PD:
 - BOR is defined as the best response across all time points from randomization until radiologically confirmed PD using RECIST, v1.1 criteria. CR is defined as the disappearance of all target and non-target lesions and any pathological lymph nodes (whether target or non-target) must have reduction in short axis to <10 mm and normalization of tumor marker level of non-target lesions. PR is defined as having a \geq 30% decrease in sum of longest diameter (LD) of target lesions. PD was defined as having a \geq 20% increase in sum of LD of target lesions and \geq 5 mm increase above nadir. SD was defined as small changes that did not meet above criteria.
- Objective Response Rate (ORR):
 ORR is defined as the percentage of participants with confirmed CR or confirmed PR.
- Clinical Benefit Rate (CBR):
 CBR is defined as percentage of combined patients who have achieved confirmed CR,
 PR and SD.

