12.0 MEASUREMENT OF EFFECT

12.1 Antitumor Effect – Solid Tumors

For the purposes of this study, patients should be re-evaluated for response every 8 weeks regardless of dosing/cycle delays. In addition to a baseline scan, confirmatory scans should also be obtained not less than 4 weeks following initial documentation of objective response.

Page 40 of 64

Information from lesion evaluation by imaging done as part of routine care will be collected until progressive disease has been objectively determined if the patient discontinued treatment due to any other reason than progressive disease.

Response and progression will be evaluated in this study using the new international criteria proposed by the revised Response Evaluation Criteria in Solid Tumors (RECIST) guideline (version 1.1).⁴¹ Changes in the largest diameter (unidimensional measurement) of the tumor lesions and the shortest diameter in the case of malignant lymph nodes are used in the RECIST criteria.

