Target lesions: All measurable lesions up to a maximum of 2 lesions per organ and 5 lesions in total, representative of all involved organs, should be identified as target lesions and recorded and measured at baseline. Target lesions should be selected on the basis of their size (lesions with the longest diameter), be representative of all involved organs, but in addition should be those that lend themselves to reproducible repeated measurements. It may be the case that, on occasion, the largest lesion does not lend itself to reproducible measurement in which circumstance the next largest lesion which can be measured reproducibly should be selected. A sum of the diameters (longest for non-nodal lesions, short axis for nodal lesions) for all target lesions will be calculated and reported as the baseline sum diameters. If lymph nodes are to be included in the sum, then only the short axis is added into the sum. The baseline sum diameters will be used as reference to further characterize any objective tumor regression in the measurable dimension of the disease.

Non-target lesions: All other lesions (or sites of disease) including any measurable lesions over and above the 5 target lesions should be identified as non-target lesions and should also be recorded at baseline. Measurements of these lesions are not required, but the presence, absence, or in rare cases unequivocal progression of each should be noted throughout follow-up.

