12.4 Response Criteria

12.4.1 Evaluation of Target Lesions

Complete Response (CR): Disappearance of all target lesions. Any pathological lymph nodes (whether target or non-target) must have reduction in short axis to <10 mm.

Partial Response (PR): At least a 30% decrease in the sum of the diameters of target lesions, taking as reference the baseline sum diameters.

Progressive Disease (PD): At least a 20% increase in the sum of the diameters of target lesions, taking as reference the smallest sum on study (this includes the baseline sum if that is the smallest on study). In addition to the relative increase of 20%, the sum must also demonstrate an absolute increase of at least 5 mm. (Note: the appearance of one or more new lesions is also considered progressions).

Stable Disease (SD): Neither sufficient shrinkage to qualify for PR nor sufficient increase to qualify for PD, taking as reference the smallest sum diameters while on study.

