12.4.2 Evaluation of Non-Target Lesions

Complete Response (CR): Disappearance of all non-target lesions and normalization of tumor marker level. All lymph nodes must be non-pathological in size (<10 mm short axis).

Note: If tumor markers are initially above the upper normal limit, they must normalize for a patient to be considered in complete clinical response.

Non-CR/Non-PD: Persistence of one or more non-target lesion(s) and/or maintenance of tumor marker level above the normal limits.

Progressive Disease (PD): Appearance of one or more new lesions and/or unequivocal progression of existing non-target lesions. Unequivocal progression should not normally trump target lesion status. It must be representative of overall disease status change, not a single lesion increase.

Although a clear progression of "non-target" lesions only is exceptional, the opinion of the treating physician should prevail in such circumstances, and the progression status should be confirmed at a later time by the review panel (or Principal Investigator).

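### Section 15.3 defines progressive and stable disease from target-lesion diameters alone, which conflicts with Sections 12.2 and 12.4 and could miscode BOR and CBR if applied literally

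*Combined protocol and SAP*

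**What the plan says.** **Section 15.3.** BOR is the best response over all time points "until radiologically confirmed PD using RECIST, v1.1 criteria". The same bullet then writes out the categories:

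- CR covers more than target lesions: "CR is defined as the disappearance of all target and non-target lesions", with a nodal short-axis condition and marker normalisation.
- PR is a fall of at least 30% in the sum of longest diameters (LD) of target lesions.
- PD is a rise of at least 20%, an "increase in sum of LD of target lesions", together with at least 5 mm above nadir.
- SD is the remainder: "SD was defined as small changes that did not meet above criteria".

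Neither new lesions nor non-target progression appears in the PD or SD sentence.

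**Section 12.** Section 12.1 sets RECIST 1.1 for the whole study: "Response and progression will be evaluated in this study using the new international criteria". Section 12.4.1 adds to the target-lesion rule that "the appearance of one or more new lesions is also considered progressions". Section 12.4.2 defines non-target PD as "Appearance of one or more new lesions and/or unequivocal progression of existing non-target lesions". The table in 12.4.3 gives overall PD for any new lesion or any non-target PD, whatever the target lesions show. It allows CR, PR or SD only when there are no new lesions. On nodes, Section 12.2 says: "If lymph nodes are to be included in the sum, then only the short axis is added into the sum".

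**Endpoints that use these categories.** ORR is confirmed CR plus confirmed PR. CBR adds SD. PFS (15.2) and TTP (15.3) take PD directly from RECIST v1.1.

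**The concern.** Section 15.3 is the only place in the statistical section that says how BOR is coded. It names RECIST v1.1 and then writes explicit rules that are narrower. The CR sentence mentions non-target lesions and the PD sentence does not, so a programmer could take the difference as intended.

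The omitted routes matter in this population. Section 3.2 admits patients with malignant ascites, and Section 12.2 classes ascites and effusions as non-measurable. Progression at those sites can be recorded only as non-target or new-lesion progression, which is the part missing from 15.3.

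What is at stake is agreement between endpoints. The same scan could make a patient a PFS event under 15.2 and a stable-disease patient under 15.3, and so a success in CBR. For nodes, 15.3 calls for a sum that the planned data may not support, because 12.2 has only the short axis of a node measured at baseline and in follow-up.

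**Working it through.** **Step 1. Is there a plan figure to reproduce?** None for this point: the documents give no target, null rate, expected rate or test for BOR, ORR or CBR. The only design figure is the 85% power for PFS in Section 15.1. It can be checked to show that it does not depend on response coding.

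- Inputs (15.1): N = 40; exponential medians 2.5 and 4 months; 12 months' accrual (taken as uniform) plus 12 months' follow-up; one-sided 0.05; one-sample log-rank test.
- Hazard ratio = 2.5/4 = 0.625.
- Event probability under the alternative, p1 = 0.947. Expected events per patient under the null hazard, p0 = 0.947/0.625 = 1.516. Difference = 0.568.
- Power = Φ[(√40 × 0.568 − 1.645 × √1.516)/σ1], where σ1 = 1.470 is the exact standard deviation under the alternative. This is Φ[(3.595 − 2.025)/1.470] = Φ(1.068) = 0.857.
- The same formula needs 38.98, so 39 patients, for 85%. The stated figure is reproduced, and no BOR category enters it.

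**Step 2. The two sets of rules side by side.**

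| Finding at a scan | 15.3 read literally | 12.4.1–12.4.3 |
|---|---|---|
| Target sum up ≥20% and ≥5 mm | PD | PD |
| Target sum stable, new lesion | SD | PD |
| Target sum stable, unequivocal non-target progression | SD | PD |
| Target sum down ≥30%, new lesion | PR | PD |
| Target lesion is a node | longest diameter | short axis (12.2) |

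Rows 2 to 5 conflict.

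**Step 3. Which patients could change category?**

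- *CBR.* A patient with SD, PR or CR recorded at an earlier scan keeps that as BOR under either reading. Only patients whose new-lesion or non-target progression appears before any such record are affected, in practice at the first 8-week scan.
- *ORR.* A patient would need at least 30% shrinkage, confirmed, despite a new lesion or non-target progression. Section 12.1 puts the confirmatory scan at least 4 weeks after the first. The BOR window in 15.3 ends at RECIST v1.1 PD, so if that progression is present at the first responding scan, confirmation falls after the window has closed.
- *PFS and TTP.* No change: both cite RECIST v1.1 PD directly.

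**Step 4. Size per patient.** Assume all 40 patients are in the denominator. One miscoded patient moves CBR by 1/40 = 2.5 percentage points, two by 5 and four by 10. Section 5.3 can remove some patients from response evaluation; a smaller denominator would make each step slightly larger. Under the rules in 12.4 the number miscoded is 0.

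**The case against.** The strongest defence is that RECIST 1.1 already governs. The BOR bullet invokes it, Section 12.1 applies it throughout, and the study calendar in Section 10 schedules a RECIST 1.1 time-point response with imaging. If BOR is taken as the best of those recorded responses, new and non-target lesions are already accounted for and nobody is miscoded. The SD sentence also speaks of small changes, which does not naturally describe a new metastasis, and the fuller CR sentence suggests abbreviated RECIST rather than a deliberate target-only system.

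Most of this stands. It means that miscoding is a possibility under literal use of 15.3, not an expected result. It does not make the sentences correct. A written PD rule that omits two of the routes in 12.4, and an LD sum where 12.2 requires the short axis, remain contradictions in an endpoint definition.

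Two stronger readings are tempting:

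- *That ORR and CBR will be inflated.* The documents do not support this. It requires the analyst to set aside RECIST in the same bullet, Section 12.1 and the 12.4.3 table. For ORR it also requires confirmed shrinkage despite progression.
- *That CBR would be overstated by 8 to 20 points.* One can take PFS events by the first scan (8 weeks, about 1.84 months): 1 − exp(−ln 2 × 1.84/4) = 0.273, or 10.9 of 40, up to 1 − exp(−ln 2 × 1.84/2.5) = 0.400, or 16.0 of 40. Multiplying by an assumed 30% to 50% share progressing only by new or non-target lesions gives 3.3 to 8.0 patients. That share has no source in the documents. PFS events include deaths without a scan, which cannot move from PD to SD. The upper end uses the historical-control median rather than the 4 months assumed for treatment.

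**Conclusion.** The PD and SD sentences in Section 15.3 are wrong as written: they conflict with 12.4.1 to 12.4.3 on new and non-target lesions, and the LD sums for PR and PD conflict with 12.2 on nodes. The consequence is conditional. Only if 15.3 is applied literally could a patient with stable target lesions and new-lesion or non-target progression at the first scan be coded SD, counted in CBR, and still be a PFS event.

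The size is 2.5 CBR points per such patient, assuming a denominator of 40. The number of such patients cannot be derived from the documents, so no total should be quoted. The ORR effect is likely negligible. BOR, ORR and CBR are secondary with no stated test, and the primary PFS analysis and the sample size do not change. This is worth correcting before analysis, but it does not threaten the trial's main conclusion.

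**What to change.** In Section 15.3, replace the CR, PR, PD and SD sentences with: *as defined in Sections 12.4.1 to 12.4.3 (target, non-target and new lesions; short axis for nodes)*.

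Add that CR and PR must be confirmed for BOR, ORR and CBR, notwithstanding the footnote to the 12.4.3 table. That footnote limits confirmation to non-randomized trials whose primary endpoint is response. The primary endpoint here is PFS, so a bare cross-reference could remove the confirmation that Section 2.2 requires for all three measures.

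The cost is one amended sentence and one added clause. No new data are needed: Section 12.2 already has non-target lesions followed and nodes measured by short axis, and the calendar already collects RECIST 1.1 time-point responses.

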15.4 Anticipated Findings

We anticipate prolongation of PFS with combination of irinotecan and ramucirumab. This may provide an early signal of activity of this combination in second line treatment of esophagogastric adenocarcinomas, and would lay the foundation for future phase III studies.

15.5 Exploratory Analyses

For PDX/PDO models, successful generation would be defined by growth in size/number ability to expand, and ability to passage. Treatment response will be assessed by cell death by counting or using a cell death assay. The correlation coefficient from the PDX and PDO models will be compared with the clinical outcome from the patients (progression vs no progressive disease) using a point biserial model which will give us a measure on the strength of the relationship between the two variables. Paired analyses for correlation will be underpowered (67% power to detect effect size of 0.6 and 10% significance level under null hypothesis of a medium effect size of 0.3 with 10 paired samples). Therefore, all analyses will be descriptive and hypothesis generating in nature, and it will be used to guide future clinical trial development incorporating PDX/PDO models.

For circulating biomarkers, levels of plasma-based biomarkers will be presented in descriptive summary. Spearman correlations among analytes may be calculated and illustrated. The prognostic value of each analyte as a continuous measure may be assessed by a univariate Cox proportional hazards model for PFS with corresponding hazard ratios and 95% confidence intervals. Cox regression analyses with each analyte adjusting for clinical variables, including age, race, gender and performance status may be performed.

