9.1.5 PDX and PDO treatment

For treatment of PDX models, after maturation of xenografts, athymic nude mice will be treated with ramucirumab (27 mg/kg) every 3 days for 3 weeks and irinotecan (40 mg/kg according to previous studies^{30,31}). Tumors will be measured twice weekly with calipers, and tumor volumes will be calculated.

For treatment of PDO models, one day after splitting, tumor organoids will be treated with ramucirumab and irinotecan diluted according to a seven-point half-log scale, with a concentration range spanning patients' therapeutic levels²⁸. For each biological run, raw data from three technical replicates across three plates will be averaged and compared with the mean of the positive control (10mM MG132) and negative control (DMSO). The effect of the drugs on the tumor organoids, in terms of cell viability, will be quantitated using a Cell titer-Glo 2.0 assay (Promega). Dose response curves, absolute IC50 and AUC will be calculated.

Based on further molecular characterization as noted below, additional therapeutic agents may be used to treat these models.

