15.0 STATISTICAL CONSIDERATIONS

15.1 Design and Sample Size

This is a multi-institutional, open-labeled, Phase II study. The study will be conducted at five institutions (including Washington University). Patients with previously treated, metastatic esophagogastric adenocarcinomas will be assigned to treatment with irinotecan plus ramucirumab.

Target sample size for this single arm, phase II study would be **40 patients**. A sample size of 40 has 85% power at a 0.050 significance level to detect a median progression-free survival time of 4 months in the treatment group when the median survival time of the

historic control group is 2.5 months. These estimations are based on historical data from irinotecan studies and a PFS improvement of 1.5 months seen in the RAINBOW study (PFS for paclitaxel alone = 2.9 months, paclitaxel plus ramucirumab = 4.4 months). Calculation is based on one-sided, one-sample log-rank test and assumes that subjects will be accrued for a period of 12 months, and follow-up continues for a period of 12 months after the last subject is enrolled.^{42,43} The survival time distributions of both groups are assumed to follow an exponential distribution.

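### Section 15.5 correlates the PDX/PDO readout with an untimed yes/no progression outcome, although PFS times and tumour diameters already collected would carry more information

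*Combined protocol and SAP*

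**What the plan says.** All references are to the combined protocol and SAP.

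- **Patient outcome.** Section 15.5 states that the coefficient from the models will be "compared with the clinical outcome from the patients (progression vs no progressive disease) using a point biserial model". No time point is attached, and nothing says how a death without documented progression is classed. This is the only method given for comparing model with patient.
- **Size and status.** The same paragraph quotes "67% power to detect effect size of 0.6 and 10% significance level"; the calculation is made "under null hypothesis of a medium effect size of 0.3 with 10 paired samples". It calls the analysis underpowered, and concludes that "all analyses will be descriptive and hypothesis generating in nature".
- **Model readout.** Section 15.5: "Treatment response will be assessed by cell death by counting or using a cell death assay". Section 9.1.5, for PDX: "Tumors will be measured twice weekly with calipers, and tumor volumes will be calculated". For PDO, 9.1.5 uses a viability assay summarised by IC50 and AUC.
- **Patient data available.** Measurable disease is required (3.1), imaging is every 8 weeks up to one year (10.0, 12.1), and the sum of target-lesion diameters is recorded (12.2). PFS is censored at 12 months (12.4.5, 15.2).
- **PFS assumptions.** Section 15.1 sizes the trial to "detect a median progression-free survival time of 4 months in the treatment group" against a null stated as "historic control group is 2.5 months", both exponential.
- **Purpose.** Section 1.7.1 describes a pilot comparing drug efficacy in the models with the patient's actual response.

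**The concern.** A point-biserial coefficient needs patients in both outcome groups. In a disease with a median PFS of a few months, whether a patient has progressed depends heavily on when the question is asked, and 15.5 does not say when. A late reading could leave almost everyone in one group. An early reading gives a workable split but still reduces a graded response to two classes, although the model readouts in 9.1.5 are continuous and the trial records both diameters and PFS times. With about 10 pairs there is little information to spare. Leaving the time point open also means it could be chosen after the data are seen.

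What is at stake is how interpretable the pilot's one stated model-versus-patient comparison will be. The efficacy conclusions of the trial are not at stake.

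**Working it through.** **The plan's own figure.** Section 15.5 states 67% power (null 0.3, alternative 0.6, 10% level, 10 pairs; sidedness not given). By Fisher's z, one-sided: (atanh 0.6 − atanh 0.3) × √7 = (0.693 − 0.310) × 2.646 = 1.015, and Φ(1.015 − 1.282) = 39%. Two-sided it is about 27%. Noncentral t gives 46% and 30%, and simulation of a bivariate normal pair gives 42% and 28%. The 67% is therefore not reproduced with a null of 0.3. This is a separate matter, and nothing below depends on it.

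**Share with a PFS event by time t.** Under the exponential assumption of 15.1 this is 1 − 2^(−t/median). Eight weeks is 56/30.4375 = 1.84 months and 16 weeks is 3.68 months.

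| Time | Median 4 months | Median 2.5 months |
|---|---|---|
| 8 weeks | 27% | 40% |
| 16 weeks | 47% | 64% |
| 12 months | 87.5% | 96.4% |

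**Reading A: status over the 12-month PFS window.** Alive and progression-free: 2^(−12/4) = 12.5%, or 2^(−12/2.5) = 3.6%.

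- Expected number among 10 pairs: 1.25 or 0.36.
- Chance of none, so that the coefficient is undefined: 0.875^10 = 26%, or 0.964^10 = 69%.
- Chance of at most one: 64% or 95%.

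These fractions count deaths as progression. If deaths without PD went into the other group, the split would be less extreme, so at this horizon the figures are upper limits.

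**Reading B: PD at an early scan or as best response.** Using the first-scan event fractions, the chance that none of 10 patients has progressed by 8 weeks is 0.727^10 = 4% (median 4) or 0.600^10 = 0.6% (median 2.5). The coefficient is usually computable.

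**Loss from splitting the outcome.** If the pair is bivariate normal and a share p falls on one side of the cut, the fraction of the correlation retained is φ(z_p)/√(p(1−p)). An underlying correlation of 0.6 is used for illustration.

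| Split | Retained | 0.6 becomes |
|---|---|---|
| 12 months, median 4 | 0.62 | 0.37 |
| 12 months, median 2.5 | 0.42 | 0.25 |
| 8 weeks, median 4 | 0.75 | 0.45 |
| 8 weeks, median 2.5 | 0.79 | 0.47 |
| 16 weeks, median 4 | 0.80 | 0.48 |
| 16 weeks, median 2.5 | 0.78 | 0.47 |

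The loss under Reading B is therefore about 20% to 25%.

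**Simulated power.** With an underlying correlation of 0.6, a null of 0, 10 pairs and one-sided 10%, power is 76% for a continuous outcome. It is 54% (median 4) or 59% (median 2.5) for the 8-week split, and 38% or 16% for the 12-month split, with undefined samples counted as no rejection. The null of 0 is chosen for illustration and is not the plan's 0.3.

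**Model side.** Cell death in 15.5 and viability in 9.1.5 are closely related for PDO. For PDX, cell death and caliper volume are different measurements.

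**The case against.** A reader might infer that the outcome will be almost constant and the analysis not computable. The documents do not support that as a general statement. Section 15.5 names no 12-month horizon; that horizon belongs to the PFS and TTP censoring rules. The stated aim is comparison with treatment response, and 15.3 already separates PD from CR, PR and SD as best response, which would give a usable split. Section 15.3 also treats death before progression as a competing risk for TTP, so PFS event fractions overstate the share with PD. These objections stand, and they limit the 26% and 69% to one reading.

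A reader might also infer that a model tracking the patient well would look weak. On an early-scan reading that is too strong. A fall from 0.6 to about 0.45 to 0.47 is small beside the sampling error with 10 pairs, where an observed 0.6 has an approximate 95% Fisher interval of −0.05 to 0.89.

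Percent change in diameters is not simply better either. It misses progression by new or non-target lesions and is absent for patients never scanned after baseline. An 8-week binary outcome has its own weakness: at a 4-month median, at most one of 10 patients would have progressed in about 20% of samples (0.041 + 0.155).

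Finally, the plan itself calls the analysis underpowered and descriptive. That limits the importance of the point. It does not supply the missing time point or the rule for deaths, and a small sample is a reason to keep the graded information.

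**Conclusion.** The point holds in a limited form. Section 15.5 relates the model readout to an untimed binary outcome when existing data allow a better measure.

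- On the 12-month reading, the coefficient could be undefined in up to about 26% (median 4 months) or 69% (median 2.5 months) of samples of 10.
- On an early-scan reading, and similarly for a best-response reading with a comparable split, it is usually computable but keeps only about 75% to 80% of the underlying correlation.

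The first result rests on the protocol's exponential medians with deaths counted as events. The second rests on bivariate normality, which is an assumption made here. The documents do not establish which reading is intended. They do not show a contradiction on the PDO side; only the PDX readout clearly conflicts between 15.5 and 9.1.5. No primary or secondary result is affected.

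**What to change.** Reword 15.5 so that the main model-versus-patient measures, all reported descriptively, are:

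1. Concordance of the continuous readout (PDX: change in tumour volume; PDO: dose-response AUC) with PFS time. This takes in new-lesion progression, deaths, and patients without a post-baseline scan.
2. The Spearman correlation of the same readout with best percent change in the sum of target-lesion diameters, among patients with a post-baseline scan.

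If a binary summary is kept, define it as PD or death at or before a named scan. Replace the cell-death wording for PDX with the caliper volume of 9.1.5.

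The cost is a change of wording in 15.5; the data are already collected, and 15.5 already uses Spearman correlation and models PFS for the blood biomarkers. The drawback is that percent change is missing for unscanned patients and does not reflect new lesions, so measure 2 must be read alongside measure 1. With about 10 pairs, both will remain imprecise.
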